#### \* \* \* Radioisotopes or Radiation Machines \* \* \*

You have not selected the Radioisotopes option in the General Checklist. If you would like to add Radioisotopes information, please select the option to enable this section.

#### 4. Radioisotopes or Radiation Machines

In this section, investigators must enter all radiation usage associated with the protocol.

Important: Protocols that involve non-standard of care radioactive materials (which includes the terms "radioisotopes", "radionuclides", "radiopharmaceuticals", and "nuclear medicine studies", e.g., "PET", "MUGA", "Zevalin", and/or specific radionuclides such as "F-18", "Tc-99m", "Th-201", "I-131", "Ra-233", "Y-90", etc.) will receive review by the Radiation Safety Officer (RSO) and/or Radiation Safety Committee (RSC). In these cases, submission to the RSO/RSC should occur after the IRB staff has drafted the informed consent radiation exposure risk statement, or verified the statement that was drafted by the research team (as noted below\*). For more information on how to submit for radiation safety review, see RSC instructions or contact the Radiation Safety Officer at [name].

**Protocol Title:** Effect of knee pain on walking biomechanics

---

Officer at [name].

(1) It is the responsibility of the PI to assure the accuracy and completeness of the data submitted in this section, consistent with guidelines provided below. (2) For projects requiring radiation procedures, please refer to this guidance.

a) If applicable, list and quantify the radiographic diagnostic and therapeutic procedures associated with this protocol by clicking "Add" and adding to Table 1 below. (Includes X-ray, fluoroscopy, CT, radioactive materials, nuclear medicine, PET-CT, radiation oncology, accelerator, Cyber Knife procedures, etc.)

b) Total estimated research radiation dose \* :

\* Calculate from the table above by adding the Effective Dose Subtotals for all procedures.

\*NOTE: Informed Consent Radiation Exposure Risk Statement- The appropriate Informed Consent Radiation Exposure Risk Statement template language must be inserted into the SLU IRB Informed Consent, inclusive of applying the total estimated research radiation dose specified in item b) from the table above, as instructed in the SLU IRB Informed Consent Template. Per IRB Guidelines, the language will either be drafted by the IRB staff or drafted by the research team and then verified by IRB staff prior to submission to the RSC for review. Contact the IRB Office at [name] or [[contact]](mailto:[contact]) with any questions.

---

\*\*\* Devices \*\*\*

**5. Devices**

a) Please list in the space below all investigational devices to be used on subjects during this study.

b) Please list in the space below all FDA approved devices to be used on subjects during this study.

**FDA Approved Devices**

Protocol Title: Effect of knee pain on walking biomechanics

Device Name	Manufacturer	Provide IDE #. Documentation of IDE # required unless imprinted on sponsor protocol (attach in section #16).
LOGIQ E10 Ultrasound System	GE Medical Systems Ultrasound and Primary Care Diagnostics, LLC	

## \*\*\* Drugs, Reagents, Chemicals, or Biologic Products \*\*\*

## 6. Drugs, Reagents, Chemicals, Biologic Products, or Dietary Supplements, Vitamins, and Other Food Agents

Pilot  
Phase IIIPhase I  
Phase IVPhase II  
Not Phased

List placebo if it is considered a drug (contains more than inactive ingredients). For example, normal saline is considered a drug that should be listed, whereas placebo tablets are usually inert ingredients that do not need to be listed.

- b) Please list in the space below all investigational drugs, reagents or chemicals to be administered to subjects during this study. Attach all applicable Investigator Brochures in section #16 (Attachments).
- c) Please list in the space below all FDA approved drugs, reagents, chemicals to be administered to subjects during this study. Attach all applicable package inserts in section #16 (Attachments).

## FDA Approved Drugs, Reagents, Chemicals, Biologic Product

Drug Name	Manufacturer	Source (e.g., Pharmacy, Sponsor, etc.)	Dosage
Lidocaine Hydrochloride	Hospira, Inc.	McKesson Corp.	1%, 10 mg/mL

- d) Please list in the space below all dietary supplements, vitamins, minerals, or foods to be administered to subjects during this study.

## \*\*\* Other Levels Of Review \*\*\*

## 7. Other Levels Of Review

Protocol Title: Effect of knee pain on walking biomechanics

**1. University Radiation Safety**

Protocols that involve non-standard of care radioactive materials (which includes the terms "radioisotopes", "radionuclides", "radiopharmaceuticals", and "nuclear medicine studies", e.g., "PET", "MUGA", "Zevalin", and/or specific radionuclides such as "F-18", "Tc-99m", "Th-201", "I-131", "Ra-223", "Y-90", etc.) will receive review by the Radiation Safety Officer (RSO) and/or Radiation Safety Committee (RSC). For information on how to submit for radiation safety review, see RSC [instructions or contact the Radiation Safety Officer at [name].](https://www.slu.edu/research/faculty-resources/research-integrity-safety/documents/irb-protocols-requiring-rsc-review-instructions-for-coordinators.pdf)

**Not Applicable**  
**Yes, study involves radioactive materials**

**2. Institutional Biosafety**

Experiments involving the deliberate transfer of Recombinant or Synthetic Nucleic Acid Molecules (e.g., Gene Transfer), or DNA or RNA derived from Recombinant or Synthetic Nucleic Acid Molecules, or Microorganisms containing Recombinant or Synthetic Nucleic Acid Molecules and/or infectious agents (including select agents and toxins as defined by CDC and/or Animal and Plant Health Inspection Service (APHIS)) into one or more human research participants must be reviewed by the SLU Biological Safety Officer. Most of these protocols also require review and approval by the SLU Institutional Biosafety Committee (IBC). Please contact the SLU Biological Safety Officer at [name] for more information.

**Not Applicable**  
**Yes, study requires Institutional Biosafety review**

**3. Pharmacy, Therapeutics, Nutrition, and Transfusion (PTNT) Committee**

Saint Louis University Hospital requires that all research involving the administration of medications within the hospital (including outpatient areas such as the Emergency Department, Outpatient Center, Saint Louis University Hospital-South Campus, etc.) be reviewed and approved by the Pharmacy, Therapeutics, Nutrition, and Transfusion (PTNT) Committee and that study drugs are received, stored, prepared, and dispensed by the Hospital's Department of Pharmacy Services. Please contact the Investigational Drug Services Clinical Pharmacist at [name] or [[contact]](mailto:[contact]) for more information.

**Not Applicable**  
**Yes, study requires PTNT review**

**4. Saint Louis University Hospital**

All research involving Saint Louis University Hospital, including the Emergency Department, inpatient or outpatient services (including outpatient surgery at SLUH South Campus and the infusion center at the DOB) and medical record access, requires Research Business Review (RBR) and approval prior to study initiation. This process is designed to facilitate compliance with state and federal regulations as they pertain to research in hospitals and clinical research billing. While researchers can begin to complete the SSM RBR form at any time, the form should not be submitted until the IRB and the Clinical

Protocol Title: Effect of knee pain on walking biomechanics

complete the SSM RBR form at any time, the form should not be submitted until the IRB and the Clinical Trials Office (CTO) have approved the study. Please contact the Research Compliance Office at [name] or [contact] or the CTO at [name] or [contact] for more information.

Not Applicable  
Yes, study requires Saint Louis University Hospital review

## 5. SSMSL

All research involving SSMSL locations (including Cardinal Glennon), including inpatient or outpatient services and medical record access, requires approval from the SSM STL or SSM Cardinal Glennon Research Business Review (RBR) prior to study initiation. This process is designed to facilitate compliance with state and federal regulations as they pertain to research in hospitals and clinical research billing. While researchers can begin to complete the SSM RBR form at any time, the form should not be submitted until the IRB and the CTO have approved the study. Please contact the SSMSL Office at [name] or [contact] for more information.

Not Applicable  
Yes, study requires RBR review

6. Does this project require registration on ClinicalTrials.gov, and/or is this project subject to the NIH GCP Training Requirement? (Select "Yes" if either apply)  Y

Registration may be required if any of the following apply: 1) The project meets the FDAAA definition of an "Applicable Clinical Trial", which requires registration on ClinicalTrials.gov. 2) As of January 1, 2017, a new NIH policy mandated biomedical and behavioral "Clinical Trials" to be registered on ClinicalTrials.gov. In addition, NIH policies require personnel on NIH "Clinical Trials" to take GCP training every three years. 3) Registering may be required for Journal Publication (ICMJE). Please review relevant definitions here. Contact the CTO at [contact] with questions about registering on ClinicalTrials.gov and refer to the training page of the IRB website for information on NIH GCP Training requirements.

## \*\*\* Subject Population \*\*\*

8. Subject Population - In the space below, please detail the participants that you are requesting to recruit (include description of each group requested)

a) Expected age range of subjects. (For example  $\geq 18$  yrs to 90 yrs).

Participants must be at least 45 years old to qualify.

b) Number of evaluable subjects to be accrued at SLU or SLU site (this includes all sites under the direction of the SLU PI).

Protocol Title: Effect of knee pain on walking biomechanics

Exceeding the number listed here is a protocol violation. Prior IRB approval is required if additional participants are to be accrued. If applicable, this number should be consistent with your power analysis described in 3d.

c) Number of evaluable subjects to be accrued study wide. \*?HELP?\* 60

d) If including vulnerable populations (minors, pregnant women and fetuses, neonates, non-English speaking, economically or educationally disadvantaged, prisoners, adults temporarily or permanently unable to consent for themselves): 1) provide the rationale for the importance of including this population in the research, and 2) specify the measures being taken to minimize risks to potentially vulnerable subjects. Click on hyperlinks to access SLU Guidelines containing additional considerations and strategies for mitigating risks.  
N/A, no vulnerable populations will be included in this study.

e) If women, minorities, or minors are not included, a clear compelling rationale must be provided unless not applicable. Examples for not including minors: disease does not occur in children; drug or device would interfere with normal growth and development; etc. If federally funded reference appropriate section of the sponsors protocol/grant. \*?HELP?\*  
Minors will not be included because knee OA is rare in minors and because the clinical definition of knee OA used in this study requires participants to be at least 45 years old.

f) If any specifically targeted subjects are students, employees, or laboratory personnel, specify the measures being taken to minimize the risks and the chance of harm to these potentially vulnerable subjects. See SLU Guidelines for additional considerations and strategies for mitigating risks.

g) Describe (labeled a-c): a) who you are recruiting for this study (e.g., your patients/students/colleagues, those in existing database or registry, the general public), and b) how you are recruiting (flyers, advertisements, direct call/mailing, membership networks, in-person recruitment in clinic, classroom, public locations, etc.). For secondary data analysis or specimen studies, state how you have access to materials. Importantly: do not contact participants prior to obtaining IRB approval for your study.

c) Also indicate whether or not you plan to obtain personal/private information or biospecimens for the purpose of screening, recruiting, or determining eligibility of prospective subjects prior to obtaining informed consent and how (obtained by communicating with prospective subjects or obtained by accessing records or stored biospecimens). Note: if you are accessing medical records other than those of your own patients or those in your immediate department, you will need to submit a HIPAA Preparatory to Research form and submit to the SLU Privacy Officer PRIOR to accessing records.

Please refer to the SLU IRB Recruitment Guidelines when designing recruitment strategies and upload recruitment materials to the Attachments page for IRB review. You are expected to obtain permission for individuals/organizations that assist with recruitment, and whenever possible, those assisting should share your materials with potential participants on your behalf rather than providing you with private contact information.

A) Patients as well as individuals from the St. Louis metropolitan area will be recruited for this study.

B) Potential participants will be recruited through advertisements, flyers, press releases, and word-of-mouth. Advertisements will be broadcasted through social media platforms, including Facebook and Instagram. Flyers will be distributed to local physician groups, foundations, health and wellness programs,

Protocol Title: Effect of knee pain on walking biomechanics

Instagram. Flyers will be distributed to local physician groups, foundations, health and wellness programs, fitness centers, community centers, and local businesses. Press releases will be performed by SLU Marketing and Communication (MarCom) services. Word-of-mouth recruitment will occur through personal interactions with St. Louis community members. [name] will also ask his physician colleagues to send out "Dear Patient" letters describing the study.

We will also utilize Washington University's Volunteer for Health (VFH) Recruitment Enhancement Core (REC) to assist with recruiting participants. This will be limited to posting on their social media platforms (i.e., Facebook, Instagram, and "X" formally Twitter) and posting to their website.

For all recruitment strategies, potential participants will be directed to fill out the Screening Form on REDCap as the first point of contact with the research team.

C) Individuals who are interested in participating in the study will fill out the online screening form. This screening form will be hosted by a database designed in Research Electronic Data Capture (REDCap) - a secure web-based, HIPAA-compliant and FDA-approved tool for collecting and analyzing data. In addition to answering questions that determine study eligibility (see inclusion/exclusion criteria), potential participants will be asked to provide their name, email address, phone number, and mailing address. The collection of this private information is necessary for bookkeeping, quality assurance, and mailing compensation to those who participate and opt to receive their payment by mail. No study-specific code numbers will appear in this database. Rather, screenings will be auto-numbered in the order they are received (1,2,3, etc.) then for those who enroll, records will be developed in the 'Master List' and 'Project Data' REDCap databases.

\*\*\* Subject Population \*\*\*

**8. Subject Population (continued)**

Page numbers from a sponsor's protocol/grant may be referenced in 8h.

**h) Inclusion and Exclusion Criteria.**

**Identify inclusion criteria.**

Inclusion for Knee OA Cohort:

- at least 45 years old
- one knee that elicits at least 3 out of 10 pain with walking
- one knee with stiffness that lasts 0-30 minutes after periods of inactivity
- one knee with pain for at least the past 3 months

\* Note -- same knee for items 2-4 above\*

Inclusion for Healthy Cohort:

- at least 45 years old
- no lower body pain (greater than 1 out of 10 with walking) or injury within the past 6 months

**Identify exclusion criteria.**

Exclusions for Both Cohorts:

- history of knee replacement surgery
- opiate use within the past 3 months
- narcotic use within the past 3 months
- known medical condition that affects walking mechanics (besides knee OA for the Knee OA Cohort)
- known medical condition that affects pain perception
- inability to walk for 30 minutes without using an assistive device
- body weight greater than 300 pounds

Protocol Title: Effect of knee pain on walking biomechanics

- known allergy to adhesives
- high risk for a cardiovascular event (modified 2020 PAR-Q+)
- currently pregnant

Additional exclusions for Knee OA Cohort:

- anticoagulant use within the past 3 months
- intraarticular knee injection within the past 3 months
- known history of hypersensitivity to local anesthetics of the amide type
- history of lower body pain or injury, besides knee osteoarthritis, within the past 6 months
- Opposite knee has pain of greater than 1 out of 10 with walking
- Opposite knee has stiffness that lasts more than 30 minutes after periods of inactivity

i) Compensation. Explain the amount and schedule of compensation, if any, that will be paid for participation in the study. Include provisions for prorating payment.

Each participant in the Knee OA Cohort who completes the study will receive \$100.00. Each participant in the Healthy Cohort (i.e., control group without knee OA) who completes the study will receive \$50.00. Participants in the Healthy Cohort receive \$50.00 less than those in the Knee OA Cohort because they complete two fewer visits (i.e., two visits compared to four visits). If participants do not complete the entire study, they will receive \$25.00 for each completed visit. Participants will be paid in the amount owed to them with a single Amazon.com gift card at the end of their participation. Depending on the participant's preference, the gift card will either be transferred electronically via email or mailed to them. Regardless of the method of payment, gift cards will be sent to each participant within 4 weeks of their final visit. All participants will also receive a parking voucher at each visit. Parking vouchers will allow participants to park in the visitor parking garage adjacent to the Allied Health Professions Building at no cost to them.

jj) Describe who will cover study related costs. Explain any costs that will be charged to the subject.

Participants will not be responsible for any study costs. All research costs will be covered by the Academy of Orthopaedic Physical Therapy, the Rheumatology Research Foundation, [name] faculty startup funds, or the Department of Physical Therapy and Athletic Training.

k) Estimate the probable duration of the entire study including data analysis and publication. This estimate should include the total time each subject is to be involved and the duration the data about the subject is to be collected. If the study is Investigator-initiated, a timeline for individual subject recruitment, follow-up, total time for subject accrual, and data analysis for the study is required.

The time each participant in the Knee OA Cohort may spend on this research study is approximately 6 hours over a 2-week period. (Four 1.5-hour visits with at least 2 days between visits)

The time each participant in the Healthy Cohort (i.e., control group without knee OA) may spend on this research study is approximately 3 hours over a 1-week period. (Two 1.5-hour visits with at least 2 days between visits)

It is expected that all visits will take approximately 1.5 hours, regardless of cohort allocation. In certain circumstances (e.g., equipment failure/malfunction) visits may last longer. No visit will last longer than 1.5 hours without agreement from the participant.

Anticipated Timeline:

- Subject Recruitment/Data Collections- September 2022-December 2023 (4 participants/month)
- Data Processing- September 2022-December 2023 (for each data collection, processing is expected to be completed within 1 week)
- Data Analyses- September 2023- January 2024
- Dissemination of Findings- Preliminary findings may be presented at professional conferences starting Fall of 2022. Peer-reviewed manuscripts will be prepared and submitted for publication within 12 months of the final data collection.
- Secondary analyses - Deidentified data will be leveraged indefinitely for answering additional research questions and providing preliminary data in future grant proposals.

Protocol Title: Effect of knee pain on walking biomechanics

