**Please save frequently**

c) Describe the study design (e.g., single/double blind, parallel, crossover, control, experimental, observational, etc.). If the study is investigator-initiated, a timeline for individual subject recruitment, follow-up, and analysis for the study is required. Also, indicate if the subjects will be randomized.

This biomechanical study will use a repeated measures design to evaluate the effects of unilateral knee pain on contralateral knee joint loading during different types of walking. Thirty adults with unilateral symptomatic knee osteoarthritis will complete four, 1.5-hour study visits. The first and third visits will include level, inclined, and declined walking at comfortable, fast, and slow speeds. The second and fourth visits will include a 30-minute walk. There will be at least two days between visits. The only difference between each pair of visits is that one visit will involve walking with unilateral knee pain (painful walking) and the other visit will involve walking without unilateral knee pain (nonpainful walking). Individuals will be recruited based on the presence of unilateral knee pain so the painful walking will be representative of their typical walking. For the visits with nonpainful walking, the third and fourth visits, pain will be alleviated by performing an intraarticular injection with a local anesthetic (lidocaine). All walking will be performed in a three-dimensional motion capture environment on a split-belt treadmill that is instrumented with force plates.

A cohort of 30 healthy controls will complete the different walking conditions at two, 1.5-hour study visits. The healthy control group will not receive intraarticular knee injections. The purpose of this cohort is to better understand how walking mechanics in individuals with unilateral knee osteoarthritis compare to similar individuals without knee osteoarthritis.

d) If subjects will be given placebo, please justify placebo use. \*?HELP?\*

N/A

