#### Walking Evaluation:

Speed determination and treadmill familiarization. At the first visit, participants will walk on a treadmill prior to performing the experimental walking conditions. The purposes of this walk are to determine a comfortable speed for level, inclined, and declined walking, and to familiarize the participant to walking on a treadmill. The speed of the treadmill will be set to 0.8 m/s at the beginning of the walk and modified based on feedback until a comfortable speed is determined. Familiarization will be completed when the participant feels comfortable and shows no outward

Protocol Title: Effect of knee pain on walking biomechanics

signs of being uncomfortable.

Setup. For each walking evaluation, 59 motion capture markers (small plastic balls) will be attached to the participant's pelvis, legs, and feet. At the first visit, markers will be placed after the familiarization walk to provide a 10- to 15-minute break from walking. For the other three visits, markers will be placed at the beginning of the visit since walking speed and familiarization will carry over from the first visit.

Once all markers are attached, participants will be asked to stand as still as possible for up to 30 seconds and perform dynamic hip trials. For dynamic hip trials, participants will be asked to flex, extend, abduct, and circumduct their hip to approximately 20 degrees. After both of these tasks are quality checked with the motion capture system, 26 markers will be removed, leaving 33 markers for tracking motion during the walking.

Intra-articular knee injections. Once the 26 markers are removed, participants will either begin the walking on the treadmill (visits 1 and 2) or receive an intraarticular knee injection and then proceed to walking on the treadmill (visits 3 and 4). If the participant is in the healthy control group, they will never receive a knee injection. If the participant is in the OA group, they will receive a knee injection at their third and fourth visits.

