For the injections, 10 mL of 1% lidocaine hydrochloride will be put into the arthritic knee using a lateral approach. All injections will be sterile and ultrasound-guided to ensure safety and proper placement of drug within the knee joint. Within 5 minutes of the injection, the participant will experience numbness and likely significant decreases in pain. [name] and [name], licensed physicians in the School of Medicine at Saint Louis University, will perform all knee injections and monitor the participant for 15 minutes after the injections.

Walking analysis for those with knee osteoarthritis. At the first and third visits, participants will be asked to complete level, inclined, and declined walking at comfortable, fast, and slow speeds in a randomized order. The only difference between the first and third visits is that an injection of lidocaine hydrochloride will be received during the third visit before walking. Each type of walking will be performed for two minutes then immediately followed by two minutes of rest. For the inclined and declined walking, the treadmill will be set to 8.3% grade (4.8 degrees). This is the maximum gradient for public and business ramps set by the Americans with Disabilities Act, and is therefore representative of gradients that individuals with knee osteoarthritis are exposed to regularly. For the fast and slow walking at each of the gradients, the speed will be increased or decreased 20% of the comfortable walking speed determined during the familiarization walk.

In addition to the first and third visits, which involve nine types of walking, participants will walk for 30-minutes continuously at their second and fourth visits. The only difference between the two 30-minute walks is that an injection of lidocaine hydrochloride will be received during the fourth visit before walking. For these walks, participants will walk at their comfortable speed and 0% grade.

During the 30-minute walks individuals will have a functional near-infrared spectroscopy (fNIRS) cap placed on their head to monitor hemodynamic response in the cortex of the brain. fNIRS utilizes light-emitting diodes and receptors to measure blood oxygenation in the cerebral cortex (the outer portion of the brain). This is similar to how a pulse oximeter measures blood oxygenation in a finger. The overall safety of fNIRS is well established as minimal risk with a similar risk profile to conventional electroencephalography (EEG).

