**a) Electronic (Computer) Data**

Click "Add" to enter data security information for each type of electronic data that will be created in the study: anonymous/de-identified, coded, and/or identifiable (see definitions above).

To properly address this question, there should only be one listing of each type of data in the table. Depending on your project, you could have up to three types of data. See the SLU ITS Sensitive Data Guide for acceptable data security methods.

Not Applicable, No Electronic (Computer) Data

Study IRB-approved Prior to New Question (Question N/A- Grandfathered)

Electronic Data

SLU eIRB

Protocol Title: Effect of knee pain on walking biomechanics

Type of Data	Storage Location	Data Transmission Outside of SLU	Supplemental information related to above items can be entered here or leave blank:
Coded	SLU ITS managed device (computer, tablet, etc.) with encryption; SLU ITS network storage (T: drive (shared drive), U: drive (personal drive)); Collection or Storage of data in SLU REDCap	Not Applicable, I will not be sending/sharing electronic data outside of SLU	The master list REDCap database will be coded, including only the code number and the screening number. Survey/Questionnaire data will be collected directly in the project's REDCap database. Motion capture data files will be collected on SLU ITS managed devices with encryption, then backed up on ITS networks (T and/or U drives). After determined from motion capture data files, measures will be recorded and in the project's REDCap database. Ultrasound data will be collected with the ultrasound scanner. At the end of each visit, ultrasound data will be transferred to a SLU ITS managed device with encryption and backed up on ITS networks (T and/or U drives). After imaging processing, measures will be recoded in the project's REDCap database.
Identifiable	Collection or Storage of data in SLU REDCap	Not Applicable, I will not be sending/sharing electronic data outside of SLU	The screening REDCap database will include questions for determining eligibility as well as name, phone number and/or email, and mailing address.

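### Pain state follows from visit number in the OA cohort, nothing described masks those who process the motion data, and the 1-week rolling target works against masking; coding files and holding them to the last visit is a cheap improvement.

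*Combined protocol and SAP*

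**What the plan says.** Section 2(c) sets out a within-person comparison: "This biomechanical study will use a repeated measures design to evaluate the effects of unilateral knee pain on contralateral knee joint loading". It ties pain state to visit: "For the visits with nonpainful walking, the third and fourth visits, pain will be alleviated by performing an intraarticular injection". The procedures in 3(b) repeat this for every OA participant: "If the participant is in the OA group, they will receive a knee injection at their third and fourth visits". Within the first pair of visits the contrast is meant to be pain alone: "The only difference between the first and third visits is that an injection of lidocaine hydrochloride will be received during the third visit before walking". The same is said of visits 2 and 4. The randomisation described concerns the walking types inside visits 1 and 3: "level, inclined, and declined walking at comfortable, fast, and slow speeds in a randomized order".

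On data handling, the anticipated timeline in 8(k) says that for each data collection "processing is expected to be completed within 1 week". Section 11(a) says of the motion data: "After determined from motion capture data files, measures will be recorded", with the project's REDCap database as the destination. The code numbers in 11(a) and 11(c) separate identity from data. No code for visit or condition is described. The prompt in 2(c) mentions blinding among its examples, and the answer describes none. Section 3(d), on analysis, does not mention processing or masking.

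**The concern.** Hypotheses 1.1, 2.1 and 2.2 each predict a higher value in the painful condition: contralateral contact force, cumulative load, and variability of contact force. All three are computed from processed motion files. If processing involves choices, such as which strides to keep, a processor who knows the condition could make them differently in the two halves of a pair without intending to. A variability outcome is an obvious candidate, because dropping or keeping unusual strides acts on it directly.

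The design makes the condition known to participants and to the staff who run the visits. Processing is a later stage, at which that knowledge could be withheld without altering any study visit. The plan does not provide for this, and its stated schedule makes it harder.

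**Working it through.** The plan has no figure of its own to reproduce: 3(d) gives no significance level, power, effect size or SD. Three checks were made.

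**1. Does visit number determine condition?**
- Inputs: 30 OA participants and four visits each (2(c)); injection at visits 3 and 4 for all of them (3(b)).
- Planned OA visits: 30 × 4 = 120. In all 120 the visit number fixes the condition.
- The type of walk shows whether a file belongs to visits 1 and 3 (nine walking types) or to visits 2 and 4 (30-minute walk). It does not show which member of the pair it is. The visit label, date or order of arrival shows that.

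**2. Does the 1-week target let arrival order reveal the condition?**
- Inputs: processing within 7 days of each collection, four visits over about 2 weeks, and at least 2 days between visits (8(k)).
- Let g be the gap in days between visits, so the visits fall on days 0, g, 2g and 3g.
- The visit 1 file is due on day 7 and its partner, visit 3, takes place on day 2g. The visit 2 file is due on day g + 7 and its partner, visit 4, takes place on day 3g. In both pairs the first file is due before the second exists when 2g > 7, that is g > 3.5 days.

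| Gap g (days) | Visit 1 due | Visit 3 held | Visit 2 due | Visit 4 held |
|---|---|---|---|---|
| 2 | 7 | 4 | 9 | 6 |
| 3 | 7 | 6 | 10 | 9 |
| 14/3 = 4.7 | 7 | 9.3 | 11.7 | 14 |

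At the shortest gaps the two files of a pair could be processed together. At even spacing over 2 weeks they could not be if the target is met: the painful file is due first, and its position gives the condition away even if its name is coded. If files are coded, held until visit 4 and shuffled, a processor's chance of naming the condition within a pair from label and order alone falls from 100% to 50%.

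**3. What would a given bias do? (Illustration only.)**
- Assumptions, none from the documents: a paired t test, two-sided 5% level, complete data on n = 30, no true effect, and a processing shift of d SDs of the paired difference in the hypothesised direction.
- Degrees of freedom 29; critical value 2.045; noncentrality = d × √30 = 5.477d. The error rate in the hypothesised direction is the probability that a noncentral t exceeds 2.045.

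| Assumed shift d | Noncentrality | Error rate in hypothesised direction |
|---|---|---|
| 0 | 0 | 2.5% |
| 0.10 | 0.548 | 7.6% |
| 0.15 | 0.822 | 12.2% |
| 0.20 | 1.095 | 18.4% |

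Counting both tails gives 8.3% at d = 0.10 and 18.5% at d = 0.20. For scale, the same test has 80% power at about 0.53 SD, so these shifts are 0.10/0.53 = 19% to 0.20/0.53 = 38% of the detectable effect.

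**The case against.** The strongest reply is that no error is shown. The documents do not say who processes the data, whether those staff attend visits, how files are named, or how much of the processing is manual. The attached grant proposals are not part of the reviewed text and may describe masking. A reader might infer that processing is known to be done by staff who see the condition, or that results will be biased. The documents support neither. They support only that nothing described prevents a processor from knowing the condition, and that the stated schedule works against masking.

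A reader might also infer that renaming files would be enough. It would not: under rolling processing, arrival order can still identify the condition, so holding and shuffling are needed as well. Nor is the change free late in the study. Processing was scheduled from September 2022, the amendment reports that recruitment has slowed, and the attachments run to March 2024. Some files have probably been processed already, although the number accrued is not shown.

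It is tempting to extend the point to ultrasound. No stated hypothesis uses an ultrasound outcome, and the timing of imaging relative to the injection is not stated, so the point is confined to motion data.

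Finally, masked processing treats the smaller problem. Pain state is confounded with visit order, and participants and collecting staff know the condition. That objection stands in full. It limits what the change achieves but is no reason to leave this route open.

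**Conclusion.** The point holds as a cheap improvement, not as a demonstrated flaw. From the documents: pain state is fixed by visit for every OA participant, the coding described protects identity only, and at gaps above 3.5 days the 1-week target makes the painful file due before its partner exists. From inference: that processing leaves room for judgement and that file labels or dates show the visit.

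The size of any bias is unknown. The range of about 8% to 18%, against 2.5%, shows what an assumed shift of 0.1 to 0.2 SD would do at n = 30. It should not be read as an estimate of this study's error rate. Masked processing would reduce one source of bias and would leave the order confounding and the open conduct of the visits as they are.

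**What to change.** Add to 3(d):
- A script gives each motion file a random code and strips visit labels and dates. The key is kept from whoever processes the files.
- Each OA participant's files are processed in random order after that participant's last visit.
- Stride exclusions are final before visit and condition labels are merged for analysis.
- Files already processed are either re-run masked or reported as processed unmasked.

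Change the 1-week statement in 8(k) so that, for OA participants, it runs from the last visit.

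The cost is a script, a key file and some delay; no added visits, participants or equipment are needed. No extra staff are needed if someone on the team who does not process the files can hold the key. At even spacing over 2 weeks all four files fall due on day 14 + 7 = 21. The visit 1 file then waits 21 − 7 = 14 days longer, visit 2 waits 21 − 11.7 = 9.3 days, visit 3 waits 21 − 16.3 = 4.7 days, and visit 4 does not wait. Re-running earlier files is the one larger cost, and reporting them as unmasked is the alternative.
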